**8. Sources of Research Material:**

1. *Identify the source(s) of materials/data to be used in the research, such as information or specimens from medical records, databases, repositories or other sources. If a combination of these sources are used, and/or new clinical data generated, describe how the research material is acquired.*

Data on obstetrical and neonatal outcomes for all women delivered at Parkland Hospital are routinely entered into [name] obstetrical operations database. Outcomes recorded for study women and their offspring will be linked by [name], who is the only person who has access to this password protected and encrypted dataset.

2. *State whether the material or data will be obtained specifically for research purposes, or whether existing records, specimens or other data will be used. If existing records or specimens are being used, please indicate the dates from which data or samples will be extracted (start and stop dates).*

This will be a prospective, double-blind, placebo controlled trial and therefore existing records or specimens will not be used.

## 9. Recruitment Methods and Consenting Process:

1. *Indicate if the potential subjects will be patients of the investigators.*

All investigators are faculty members and oversee obstetrical care at Parkland Hospital.

2. *Describe and provide details of the recruitment process. Include when, where, by whom and how potential subjects will be approached. Indicate if non-English speaking subjects are being consented and if so, indicate how informed consent process will be conducted.*

Research nurses employed by the Department of Obstetrics & Gynecology, and who are on-call and monitoring Labor & Delivery, will identify, approach and provide informed consent to all potential participants (these tasks will be performed by [name] if a research nurse is unavailable when a patient presents with preterm labor). If potential participants are non-English speaking, a language-appropriate translator will be obtained as per current Department of Obstetrics & Gynecology research protocols.

3. *Explain measures that will be taken to respect the privacy of the potential subjects.*

Patients will generally be consented in one of the private rooms on Labor & Delivery.

4. *Explain what precautions will be taken to minimize the potential for undue influence or coercion.*

Professional research nurses already on staff with the Department of Obstetrics & Gynecology, and who do not have an interest in a particular study outcome, will be providing the informed consent during weekdays and most weeknights. If a patient presents with active preterm labor when a research nurse is unavailable, [name] will obtain informed consent. [name] has observed several of these nurses obtain informed consent in a dispassionate and thorough manner, which emphasizes to the patient that the usual care that we provide will not be affected by her decision to participate or not.

5. *If you are requesting a waiver of informed consent, explain how the criteria for waiver are met.*  
N/A

6. *If vulnerable populations will be included, describe the additional protections that will be provided, such as methods to obtain surrogate consent (cognitively impaired subjects), and plans for obtaining assent and/or the permission of one or both parents (minors).*  
N/A

## 10. Potential Risks:

1. *Describe the known risks and/or potential discomforts associated with each intervention or research procedure. Risks may be physical, psychological, social or economic.*

Mild side effects associated with nifedipine include headache, flushing and low blood pressure, which generally resolve with discontinuation of the medication and without further intervention. In a systematic review, Khan et al (2010) reported that the use of calcium channel blockers for tocolysis or for hypertension in pregnancy was associated with a 3-fold increased risk of tachycardia and an 8 to 9-fold increased risk of hypotension when the dose exceeded 60 mg per day. However, this analysis included all pregnant women receiving all different types of calcium channel blockers (including severely hypertensive women, particularly women with preeclampsia and severe gestational hypertension, a very different population that we propose to study), and thus was not limited to

women with preterm labor, the sub-population than we propose to study. Regarding the possibility of hypotension, Luewan et al (2010) studied blood pressure in normotensive pregnant women treated with nifedipine 10 mg every 15 minutes up to 40 mg, followed by 60 mg controlled release tablet in 4 to 6 hours. The authors defined hypotension as a decrease in diastolic blood pressure of at least 15 mmHg from baseline, and reported up to 17% of patients met these criteria. They concluded that “hypotension secondary to nifedipine was not associated with significant clinical symptoms, suggesting that nifedipine is relatively safe in terms of hypotensive effect.”

Houtzager et al (2006) performed long-term follow-up of children exposed in utero to nifedipine or ritodrine for preterm labor and reported: “The results do not support any differential postnatal effect of the tocolytic agents ritodrine or nifedipine on the child's long-term psychosocial and motor functioning. The slightly better outcome of children randomised in the nifedipine group is most likely due to more favourable perinatal outcomes in this group.”

More serious side effects are rare when the widespread use of nifedipine in the community is considered. In the English-language medical literature, there are 22 reported cases of pulmonary edema, 1 stillbirth and 2 cases of myocardial infarction associated with nifedipine tocolysis, but these risks were reported in association with other particular risk factors such as use with other tocolytic drugs, use of rapid-acting formulations, prolonged tocolysis and use when there was evidence of preexisting maternal cardiac disease/dysfunction (Bal et al, 2004; Vaast et al, 2004; Abbas et al, 2006; Van Geijn et al, 2005; Nassar et al, 2007; Gatault et al, 2008; ; Kutuk et al, 2013; Serena et al, 2014; Van Veen et al, 2005; Oei et al, 1999; Verhaert and Acker, 2004). The single report of stillbirth was disputed and provoked a series of follow-up letters in response to the controversy (Johnson, 2005; Kandysamy, 2005; Papatsonis et al, 2005). Importantly, in 26 published trials involving isolated use of nifedipine for acute tocolysis, there were no cases of pulmonary edema or more serious side effects among patients receiving nifedipine (References 8a-aa). More recently, Kutuk (2013) reported a case of pulmonary edema with nifedipine use in a woman with ruptured membranes at 33 weeks. The authors note that the pulmonary edema occurred on the 4th day of her admission in association with prolonged tocolysis. In this case report of a single patient, there was prolonged use of nifedipine in a woman with ruptured membranes, which was arguably not acute tocolysis at all since the event occurred during a period typically associated with maintenance tocolysis. Our study restricts use to acute tocolysis with only 48 hours' duration, and in women with intact membranes. Four other cases of pulmonary edema were reported by Serena et al (2014), but these were all in women with prolonged intravenous use of nicardipine, and intravenous tocolysis is a recognized risk factor for pulmonary edema (Oei, 2006). We are not using intravenous formulations nor will we be using nifedipine for prolonged periods (maximum 48 hours of acute tocolysis).

We plan to restrict use to healthy, normotensive women with singleton pregnancies not receiving additional tocolytic agents. We will also not use sublingual administration of nifedipine. Therefore, these reported adverse reactions are most unlikely.

2. *Estimate the probability (chance or likelihood of occurrence) that a given harm may occur and its severity (mild, moderate or severe) and define risks by percentages, when available, or by categorizing with the terms rare, unlikely, likely.*

#### Mild Events:

*Mild headache or flushing: **Likely**; Moderate headache, Dizziness or Nausea: **Unlikely***

A review (Chan et al, 2008) of nifedipine for first-line tocolysis of 212 episodes of preterm labor in 203 women reported that moderate headache was the most common side effect (9 of the 203 women, 4.4%). Other side effects included flushing (9 of the 203 women, 4.4%), dizziness (4 of the 203 women, 2%), nausea (3 of the 203 women, 1.5%), shortness of breath (1 of the 203 women, 0.5%). A study by Guclu (2006) found that up to 71% of patients had flushing and 25% had headache. A review (Marin et al, 2007) of nifedipine tocolysis in 24 patients reported that 11 (45.8%) had mild headache.

#### Moderate Events:

*Hypotension or Tachycardia: **Unlikely***

A review (Chan et al, 2008) of 203 women for whom nifedipine was prescribed as the first-line tocolytic in 212 episodes of preterm labor reported that nifedipine was discontinued for hypotension less than 90/60 in 3 women (1.5%). One woman (0.5%) developed tachycardia of at least 140 BPM.

#### *Pulmonary Edema: **Rare***

There are 8 case reports/case series (Bal et al, 2004; Vaast et al, 2004; Abbas et al, 2006; Van Geijn et al, 2005; Nassar et al, 2007; Gatault et al, 2008; Kutuk et al, 2013; Serena et al, 2014) including a total of 22 patients with pulmonary edema in the English-language medical literature. Risk factors appear to be multiple gestation, sublingual (rapid-acting) or intravenous dosing of nifedipine or

nicardipine, use of multiple tocolytics, prolonged use of tocolysis and maternal cardiac disease or dysfunction. These risk factors will be avoided due to our very specific inclusion and exclusion criteria and the non-sub-lingual formulation of nifedipine used. In an expert review of the literature, Oei (2006) recommends that intravenous nicardipine or high doses of nifedipine should not be used in cases of multiple gestation or when the mother is compromised cardiovascularly. Intravenous formulations will not be used in this study, and multiple gestations will be excluded. Importantly, in 26 published trials involving nifedipine for acute tocolysis, there were no cases of pulmonary edema among patients receiving nifedipine.

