Given the prevalence of this off-label use of nifedipine, it is unlikely that serious adverse events are commonly encountered. The main serious risk associated with nifedipine is pulmonary edema, but in the 17 reported cases, this risk was reported in the context of other specific risk factors, such as use with other tocolytic drugs, use of rapid-acting formulations, prolonged tocolysis, and use when there was evidence of preexisting maternal cardiac disease/dysfunction. Importantly, in 26 published trials involving isolated use of nifedipine for acute tocolysis, there were no cases of pulmonary edema among patients receiving nifedipine (References 8a-aa).

We plan to restrict use to healthy, normotensive women with singleton pregnancies not receiving additional tocolytic agents. We will also **not** use prolonged or sublingual (rapid acting) administration of nifedipine. Therefore, these reported adverse reactions are most unlikely. Milder side effects associated with nifedipine include headache, flushing and low blood pressure, which resolve with discontinuation of the medication. The balance of benefits and risks favors performing this study to quantify benefits, if any, given the potential for nifedipine to stop preterm labor and its high use rate in the community.

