## 2. Background:

1. *State the purpose of the research and describe the related theory/data supporting the intent of the study.*

The purpose of this research is to determine whether nifedipine is effective compared to placebo for delaying delivery sufficient to ensure delivery of corticosteroids and thus reducing preterm birth related morbidity. Nifedipine interferes in calcium transport across cell membranes and is an effective smooth muscle relaxant. We believe that uterine relaxation (tocolysis) from nifedipine may reduce preterm birth.

2. *Describe what is considered standard care (approved and/or customary) for the medical condition being studied, if applicable.*

Although tocolysis is not currently used at Parkland Hospital, it is considered within the standard of care for physicians caring for women in preterm labor.

3. *Explain how the new treatment or procedure may improve standard care, if applicable. Clearly delineate what is considered research study items from the “standard care”.*

If nifedipine is identified as an effective tocolytic for reducing preterm birth, it would be included as part of the standard care for women with preterm labor.

4. *Provide a short statement concerning the status of the drug, drug combination, delivery method, device, or other interventions/concepts to be studied.*

Nifedipine is FDA approved for treatment of angina and hypertension, but it is widely used off-label as a tocolytic for preterm labor.

5. *Indicate whether the research is confirming or an extension of previous work, or whether it is pioneering with little prior information. Include an evaluation of existing knowledge and identify the information gaps that the project intends to address.*

No placebo controlled, randomized trials of nifedipine as an intervention for acute tocolysis of preterm labor (defined as cervical dilatation with contractions) have been reported, therefore, this study will be an important contribution to the medical literature.

6. *Describe published research with animals and/or humans that supports the study hypothesis or objectives. If applicable, include information regarding toxicity. Include a bibliography of key references/citations as applicable.*

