## **6. Criteria for Inclusion of Subjects:**

1. *Describe the characteristics of the subject population. For example, list any characteristics required for eligibility, such as diagnosis, prior therapy, age, or gender.*

Inclusion criteria include:

- Mothers between 16 and 44 years of age inclusive.
- Singleton pregnancy
- Intact membranes
- Between 28-0/7 weeks and 33-6/7 weeks' gestation inclusive
- Reported or documented uterine activity
- Cervical dilation between 2 cm and 4 cm inclusive

2. *Explain the rationale for the use of special classes of subjects who are more likely to be vulnerable, such as pregnant women, children, cognitively impaired people or prisoners.*

Pregnant women are included as this study is for an intervention for preterm labor.

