**Exclusion criteria:**

Oppose inclusion criteria:

- Multifetal gestation
- Less than 28 weeks' gestation
- 34 or more weeks' gestation
- Ruptured membranes

• More than 4 cm dilated  
Corticosteroids contraindicated:

- Previously received a course of corticosteroids for fetal lung maturation

Tocolysis contraindicated:

- Low amniotic fluid (oligohydramnios)
- Fetal growth restriction
- Chorioamnionitis or temperature of at least 38.0 degrees Celsius
- Fetal death
- Preeclampsia
- Suspected placental abruption or placenta previa
- Lethal fetal malformation or amniotic fluid index at least 35

Nifedipine contraindicated:

- Systolic BP < 90 mmHg or diastolic BP < 50 mmHg
- Baseline tachycardia (pulse >120 after 2 consecutive measurements 30 minutes apart)
- Chronic hypertension treated with antihypertensives in pregnancy
- Seizure disorder or HIV\*
- Women who have received progesterone therapy in the 2nd or 3rd trimester
- Maternal allergy to nifedipine
- Known maternal cardiac disease

\* See July 2013 FDA warning regarding nifedipine and phenytoin, also several protease inhibitors are strong inhibitors of metabolizing enzyme CYP3A4

2. *Include situations or conditions, unknown at the time of enrollment that might cause a screening failure.*

No situations known.

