#### **11. Subject Safety and Data Monitoring:**

1. *Describe what measures have been taken and/or will be taken to prevent and minimize any risks or discomforts.*

Only singleton pregnancies in women with preterm labor and unruptured membranes will receive either placebo or nifedipine. Multiple tocolytics will not be used. Additionally, intravenous or sublingual (rapid-acting) forms of nifedipine will not be used. Only women with preterm labor at 28-0/7 weeks to 33-6/7 weeks will be included, as women with preterm labor between 24-0/7 weeks and 27-6/7 weeks receive magnesium sulfate for neuroprophylaxis and magnesium sulfate can synergize with nifedipine to block calcium movement through calcium channels. Women with hypotension, tachycardia or significant maternal cardiac disease or hypertension treated with antihypertensives will be excluded at the outset. Women with potential indications for delivery will be excluded. Hold dose parameters and stopping rule for further participation are detailed in Section 4(1) above.

2. *If applicable, discuss provisions for insuring necessary medical or professional intervention in the event of adverse events.*

All study participants will undergo regular vital sign monitoring while on Labor & Delivery and on the antepartum unit. Patients on Labor and Delivery will have continuous electronic fetal monitoring and tocometer evaluation, and patients on the antepartum unit will have daily fetal heart testing. If a maternal or fetal complication is identified, physicians will be immediately available to intervene on behalf of the mother and fetus.

3. Describe the plan for monitoring study data collected to protect subject safety and data integrity. Please review [Guidance on Data and Safety Monitoring Plans](#) for instructions on what information should be provided. If desired, the [DSMP Template](#) may be used and included in your application packet.

See DSMP

4. Note: investigator-initiated studies involving administration of an experimental (i.e. not FDA approved for the indication/population under study) drug, device or intervention **must** submit a Data Safety Monitoring Plan ([DSMP Template](#)) and may be required by the IRB to establish a Data Safety monitoring Board (DSMB).

See DSMP

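### The safety case credits the entry criteria with avoiding multiple tocolytics, but no criterion covers tocolytic exposure, so a dose given before arrival is not clearly screened out

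*Combined protocol and SAP*

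**What the plan says.** The pulmonary edema paragraph in Section 10, item 2 lists risk factors that include "use of multiple tocolytics, prolonged use of tocolysis and maternal cardiac disease or dysfunction". It then gives the reason why they do not apply here: "These risk factors will be avoided due to our very specific inclusion and exclusion criteria", along with the choice of a formulation that is not sublingual.

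Other sections state the same intention:

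- Section 1, item 3, repeated at the end of Section 10, item 1, limits use to healthy, normotensive women with "singleton pregnancies not receiving additional tocolytic agents".
- Section 11, item 1 says "Multiple tocolytics will not be used". The Safety part of Section 2 and the stillbirth and myocardial infarction paragraph of Section 10 say much the same.
- Section 10, item 1 says that participants will not be on magnesium sulfate.

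On practice, Sections 2 and 10 say that the hospital does not use tocolytics for preterm labor. Of tocolysis more generally, Section 2 says "it is considered within the standard of care for physicians caring for women in preterm labor", and it describes off-label use of nifedipine for this purpose as widespread.

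The nearest related entry in the exclusion list is "Previously received a course of corticosteroids for fetal lung maturation".

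**The concern.** The risk section asks the reader to accept that the published serious events do not carry over to this trial, largely because combined tocolytic exposure will not occur. For pulmonary edema it attributes that protection to the entry criteria. If the criteria do not contain it, the safeguard exists only as a stated intention. The person screening a woman on Labor & Delivery works from the list in Sections 6 and 7, not from the risk narrative.

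The route by which this could matter is narrow but follows from the plan's own account. A woman may be treated at another facility, where tocolysis is accepted practice, and then present or be transferred with a cervix of 2 to 4 cm and continuing uterine activity. Nothing in the list asks what she was given. On active drug she may have an earlier agent still acting. On placebo she is not strictly an untreated control.

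**Working it through.** No arithmetic decides this point. The check is whether the text of the criteria contains what Section 10 credits to them.

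**1. Each risk factor in the Section 10 paragraph against the safeguard that addresses it**

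| Risk factor named | Where it is addressed | In the entry criteria? |
|---|---|---|
| Multiple gestation | Singleton inclusion; multifetal exclusion | Yes |
| Sublingual or intravenous dosing | Oral capsule, Sections 3 and 4 | No, but the treatment itself settles it |
| Maternal cardiac disease or dysfunction | Exclusion for known cardiac disease | Yes |
| Prolonged tocolysis | 48-hour limit on study drug, Sections 3 and 4 | No, but the treatment schedule limits it |
| Multiple tocolytics | Narrative in Sections 1, 2, 10 and 11 | **No** |

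The formulation cannot control exposure to a second agent. For that factor the Section 10 statement therefore rests on the criteria alone.

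**2. The criteria, item by item**

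- *Inclusion (Section 6), six items:* age, singleton, intact membranes, gestational age, "Reported or documented uterine activity", and cervical dilation. None concerns prior or current treatment.
- *Exclusion (Section 7), tocolysis contraindicated:* obstetric and fetal conditions such as "Suspected placental abruption or placenta previa". None concerns a tocolytic already given.
- *Exclusion, nifedipine contraindicated:* blood pressure, pulse, treated chronic hypertension, seizure disorder or HIV, progesterone, allergy and cardiac disease. There is no item on earlier nifedipine or another tocolytic.
- *Exclusion, corticosteroids contraindicated:* a previous course. A woman given a tocolytic without steroids passes. A woman given a single steroid dose is not clearly caught, because the list does not say what counts as a course.
- *Screening steps, hold-dose rule and individual stopping rule (Section 4, the last two repeated in Section 11):* no mention of earlier tocolytic exposure.

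The exclusion list already screens treatment history for progesterone, corticosteroids and antihypertensives. An item on tocolytics would fit its structure.

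**3. What the narrative covers**

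| Situation at screening | Narrative restriction (Sections 1 and 10) | Eligibility list |
|---|---|---|
| Another tocolytic still being given | Covered | No item |
| Another tocolytic given and stopped before arrival | Not clearly covered: the wording is in the present tense | No item |
| Nifedipine given before arrival | Not clearly covered: the wording speaks of additional agents | No item |

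**4. The plan's own figure**

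Section 14 gives 75 per arm for 71.2% against 47.5%, two-sided 5%, 80% power. The pooled-variance formula for two proportions gives 67 per arm without and 75 with continuity correction, so the stated figure reproduces with the correction. An added eligibility item does not change it.

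**The case against.** The strongest reply is that Sections 1 and 10 already restrict the population. The sentence places freedom from additional tocolytics beside singleton and normotensive, which are entry conditions. A reader who sees only the eligibility list might infer that the plan permits randomising a woman with another agent still running. The documents do not support that: such a woman falls outside the stated restriction. This part of the reply stands, and it narrows the gap to treatment given before arrival and to a restriction that never reached the list.

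Three other stronger readings also fail.

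- **That every pre-treated woman on active drug carries the risk factor.** The cohort cited in Section 10, item 1 found tocolytic pulmonary edema only with simultaneous agents. Whether a dose stopped hours earlier overlaps with study drug is not something the documents settle. Nor do they show that a few hours of earlier treatment amounts to prolonged tocolysis.
- **That the first-24-hour maximum could be exceeded without breaking a trial rule.** If the maximum in Sections 3 and 4 counts all nifedipine, exceeding it breaks a rule. If it counts study capsules only, it is not exceeded. The supportable point is that the text does not say which.
- **That power falls by a known amount.** Suppose a share f of placebo women had received an agent with the full planned effect. The control rate would be (1 − f) × 71.2% + f × 47.5%. At f = 5%, 10% and 15% this is 70.0%, 68.8% and 67.6%. Power at 75 per arm would fall from 84.7% to 80.6%, 75.9% and 70.8% without continuity correction, or from 80.3% to 75.6%, 70.4% and 64.8% with it. But the shares are invented, since the documents give no rate of transfer or prior treatment. The full effect is generous too: Section 2 says that the other agents have not been shown to improve birth outcomes, and an enrolled woman must still have uterine activity at 2 to 4 cm. This is an illustration, not a magnitude.

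It is also fair that partial screens exist. The hospital gives no tocolysis, and the exclusions for a steroid course, low blood pressure and tachycardia would stop some pre-treated women. They bear on frequency, but none asks about the exposure itself.

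**Conclusion.** The point holds in a limited form. Section 10 credits the inclusion and exclusion criteria with avoiding multiple tocolytics, and they contain no item that does so. The narrative restriction covers an agent still being given. It does not clearly cover a tocolytic, including nifedipine, received before arrival.

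This is an inconsistency between the safety narrative and the eligibility list. It is worth correcting because the risk argument leans on it and the correction is cheap. It is not evidence that pre-treated women were or will be enrolled, or that anyone would be harmed. The conclusion rests only on the text of the criteria. How often it matters depends on how many women are treated elsewhere first, which the documents do not report and which may be few.

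**What to change.** Reconcile Section 1 (item 3), Section 10 (items 1 and 2) and Section 11 (item 1) with Sections 6 and 7, in one of two ways:

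- Carry the stated restriction into the eligibility list as an item on tocolytic exposure during the current episode of preterm labor, at this hospital or elsewhere. Have it checked from transfer and medication records before the pharmacy randomises. Which agents count and over what time window are for the sponsor to define.
- Otherwise, amend the pulmonary edema paragraph so that it no longer credits the criteria with avoiding this risk factor.

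In either case, state in Sections 3 and 4 whether the first-24-hour maximum counts nifedipine given before enrolment.

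The first option costs one line in the protocol and one screening check, plus whichever pre-treated women become ineligible. That is probably a few, though the documents give no count. The planned 75 per arm does not change. Recording prior tocolytic use on the screening log would supply the missing rate.
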